**Table 5-6: Schedule of study assessments - Safety Follow-Up Extension Period**

[figure not shown]
Visit #	29	30	31	32	33	34	35	36	37	38	39	40
Overall Study Week/SFE Week Protocol Activity	52/0 a	54/2	56/4	64/12	76/24	88/36	100/48	112/60	124/72	136/84	148/96	156/104/SFE-WD
Informed consent b	X											
CRP												X
BASDAI												X
BASFI												X
ASQoL												X
Total and nocturnal spinal pain												X
PGADA												X
MRI SI joints												X
AEs		X	X	X	X	X	X	X	X	X	X	X
IXRS c	X	X	X	X	X	X	X	X	X	X	X	X
Study drug loading dose administration sc,d	X	X	X									
Study drug dispensation e	X			X	X	X	X	X	X	X	X	X

AEs=adverse events; ASQoL=Ankylosing Spondylitis Quality of Life; BASDAI=Bath Ankylosing Spondylitis Disease Activity Index; BASFI= Bath Ankylosing Spondylitis Functional Index; CRP=C-reactive protein; CZP=Certolizumab pegol; FU=Follow-Up; IXRS=Interactive Response System; MRI=magnetic resonance imaging; PGADA=Patient's Global Assessment of Disease Activity; sc=subcutaneously; SFE=Safety Follow-Up Extension; SI=sacroiliac; WD=Withdrawal

- a Assessments performed at the Week 52 Visit for subjects who completed the previous Double-Blind Period are in Table 5-1; Assessments performed at the Week 52 Visit for subjects who transitioned to open-label CZP treatment after withdrawal from the Double-Blind Period are in Table 5-2.
- b A separate informed consent form will be obtained from subjects consenting to participate in the SFE Period.
- c Contact IXRS to register the visit and obtain next kit number, where applicable, or to indicate that the subject has completed the SFE Period or withdrawn from the study.
- d At Weeks 52, 54, and 56, study treatment administration should be performed at the site by unblinded study personnel in order to keep the blind (see Section 7.2.1).
- e Starting at Week 52 for subjects completing open-label CZP treatment and the Week 52 Visit, dispense the assigned study medication to the subject for use at home, as appropriate.

### 5.3 Schematic diagram

**Figure 5-1: Schematic diagram for subjects completing the double-blind study treatment**

[figure not shown]

ASDAS-MI=Ankylosing Spondylitis Disease Activity Score major improvement; axSpA=axial spondyloarthritis; BL=Baseline; CRP=C-reactive protein; CZP=certolizumab pegol; FU=Follow-Up; mNY=modified New York criteria; MRI= magnetic resonance imaging; N=number of subjects; PI=Principal Investigator; Q2W=every 2 weeks (every other week); SCR=Screening; TNFi=tumor necrosis factor- $\alpha$  inhibitor; WD=withdrawal

[figure not shown]
**Figure 5-2: Schematic diagram for subjects discontinued from the double-blind study treatment**

Scenario A: The subject initiates treatment with CZP for treatment to be supplied to discontinued subjects

At the discretion of the PI the double-blind study treatment is discontinued and treatment with CZP is initiated. The new treatment shall continue through to Week 52 of the regular visit schedule.

[figure not shown]
Scenario B: The subject initiates treatment with other treatments (including biologics)

At the discretion of the PI the double-blind study treatment is discontinued and treatment with other treatments (including biologics) is initiated. The new treatment shall continue through to Week 52 of the regular visit schedule.

BL=Baseline; CZP=certolizumab pegol; FU=Follow-Up; PBO=placebo; PI=Principal Investigator; Q2W=every 2 weeks (every other week); SCR=Screening; W=week; WD=withdrawal

**Figure 5-3: Schematic diagram for subjects completing the double-blind study treatment and rolling over to the SFE Period**

BL=Baseline; CZP=certolizumab pegol; FU=Follow-Up; SFE=Safety Extension; PBO=placebo; SCR=Screening; SFE=safety Follow-Up Extension; W=week; WD=withdrawal

Note: Subjects who complete either double-blind treatment or open-label CZP-treatment and all assessments at Week 52 are eligible to roll-over to the SFE Period. Subjects who complete alternative treatment must finish the study at Week 52 and be scheduled for the final FU visit (8 weeks after the Week 52 Visit).

## 5.4 Rationale for study design and selection of dose

The current study will evaluate nr-axSpA subjects receiving either CZP or placebo in combination with standard of care for a duration of 52 weeks. This is a unique study design to achieve an understanding of the natural history of nr-axSpA and to support the assumption that treatment with a TNFi is necessary in this group of subjects. The lack of a mandatory escape arm for placebo subjects is balanced by the ability of the Investigators to modify background medications (NSAIDs, corticosteroids, analgesics, and SAARDs) during the course of the study. If the Investigator determines that a subject should be treated with other medicines (including biologics), the study medication will be discontinued and subjects will be asked to continue to come to the office for study visits to track their response to other treatments. If the Investigator chooses to withdraw subjects on the other therapy, the local guidelines on initiation and monitoring of the particular treatment should be followed.

In accordance with prescribing information for CZP, 3 loading doses of 400mg Q2W should be administered upon initiation of therapy. Thus all subjects who withdraw from double-blind treatment prior to Week 52 and transition to open-label CZP within the AS0006 study will receive this loading dose prior to the maintenance dose of 200mg Q2W. It is recognized that some subjects would have been on active CZP prior to transition to open-label CZP. However, this dosing approach is justified in all transitioning subjects as there will be no change in benefit-risk due to administration of loading dose and the blinding will be maintained in the study, preserving the data integrity.

The enrollment criteria will result in the following subgroups based on MRI and CRP:

- MRI+/CRP+
- MRI+/CRP-
- MRI-/CRP+

This 3-level MRI/CRP classification variable will be used as a stratification factor in the randomization to ensure balance across these subgroups. Taken together, these 3 subgroups encompass the nr-axSpA subject population that would benefit most from anti-TNF therapy and who have the most limited treatment options.

## 6 SELECTION AND WITHDRAWAL OF SUBJECTS

### 6.1 Inclusion criteria

To be eligible to participate in this study, all of the following criteria must be met:

1. An Institutional Review Board (IRB)/Independent Ethics Committee (IEC) approved written Informed Consent form is signed and dated by the subject or legal representative. The
2. Subject/legal representative is considered reliable and capable of adhering to the protocol (eg, able to understand and complete questionnaires), visit schedule, or medication intake according to the judgment of the Investigator.
3. Subject is at least 18 years old at the Screening visit.

4. Female subjects must be either postmenopausal for at least 1 year, surgically incapable of childbearing, or effectively practicing an acceptable method of contraception (either oral/parenteral/implantable hormonal contraceptives, intrauterine device, or barrier and spermicide). Abstinence only is not an acceptable method. Subjects must agree to use adequate contraception during the study and for at least 10 weeks (or [for participating countries of the EU – 5 months in accordance with the Summary of Product Characteristics, SPC] longer if required by local regulations) after the last dose of study treatment. Male subjects must agree to ensure they or their female partner(s) use adequate contraception during the study and for at least 10 weeks (or [for participating countries of the EU - 5 months in accordance with the SPC] longer if required by local regulations) after their last dose of study treatment.
5. Subjects must have a documented diagnosis of adult-onset axSpA and meet the ASAS criteria for axSpA (not including family history and good response to NSAIDs; see Appendix 18.1).
6. Subjects must have had back pain for at least 12 months before Screening.
7. Subjects must NOT have sacroiliitis defined by mNY criteria (see Appendix 18.2) (bilateral  $\geq$ Grade 2; unilateral  $\geq$ Grade 3) on SI joint x-rays (based on central reading of x-rays, within the last 12 months from Baseline).
8. Subjects must have active disease as defined by each of the following at Screening and Baseline:
  - BASDAI score  $\geq$ 4
  - Spinal pain  $\geq$ 4 on a 0 to 10 NRS (from BASDAI item 2)
9. Subjects must have a combination of current evidence of sacroiliitis on the screening MRI as defined by ASAS/OMERACT scoring confirmed via central reading (MRI+) and CRP either  $>$ upper limit of normal (ULN) or  $\leq$ ULN (for CRP the ULN is defined as the ULN indicative for inflammatory disease) at Baseline (CRP+ or CRP-), or no evidence of sacroiliitis on the screening MRI (MRI-) and CRP  $>$ ULN (CRP+) as follows:
  - MRI+/CRP+
  - MRI+/CRP-
  - MRI-/CRP+
10. Subjects must have had an inadequate response to, have a contraindication to, or have been intolerant to at least 2 NSAIDs. Inadequate response to an NSAID is defined as lack of response to at least 14 days of continuous NSAID therapy at the highest tolerated dose of the administered NSAID.

## 6.2 Exclusion criteria

Subjects are not permitted to enroll in the study if any of the following criteria is met:

1. Subject has previously participated in this study or subject has previously been assigned to treatment in a study of the medication under investigation in this study.

2. Subject has participated in another study of an investigational medicinal product (IMP) (or a medical device) within the previous 3 months (or 5 half-lives, whichever is greater) or is currently participating in another study of an IMP (or a medical device).
3. Subject has history of chronic alcohol abuse or drug abuse within the last year.
4. Subject has any medical or psychiatric condition that, in the opinion of the Investigator, could jeopardize or would compromise the subject's ability to participate in this study.
5. Subject has a known hypersensitivity to any components of the IMP or comparative drugs as stated in this protocol.

#### **Axial SpA-disease-related exclusions**

6. Subjects must not have AS or any other inflammatory arthritis (eg, RA, systemic lupus erythematosus, or sarcoidosis).
7. Subject must not have fibromyalgia.
8. Subjects must not have a secondary, noninflammatory condition (eg, osteoarthritis) that in the Investigator's opinion is symptomatic enough to interfere with evaluation of the effect of study drug on the subject's primary diagnosis of axSpA.

#### **Prior medications exclusions**

9. Subjects must not have used the following medications in the manner as detailed by the exclusion criteria in the following table (see [Table 7-1](#)).

#### **Previous clinical studies and previous biological therapy exclusions**

10. Subjects must not have received any nonbiological therapy for axSpA not listed in [Table 7-1](#) within or outside a clinical study in the 3 months or within 5 half-lives prior to the Baseline visit (whichever is longer).
11. Subjects must not have received any experimental biological agents (defined as those agents unlicensed for use in axSpA in Europe or the USA).
12. Subjects must not have received previous treatment with a PEGylated compound that resulted in a severe hypersensitivity reaction or an anaphylactic reaction.
13. Subjects may not have been exposed to more than 1 TNFi prior to the Baseline visit and may not be a primary failure to any TNFi therapy (defined as no response within the first 12 weeks of treatment with the TNFi).

#### **Medical History Exclusions**

14. Female subjects who are breastfeeding, pregnant or plan to become pregnant during the study or within 3 months following the final dose of the investigational product.
15. Subjects with a history of chronic or recurrent infections (more than 3 episodes requiring antibiotics or antivirals during the preceding year), recent serious or life-threatening infection within the 6 months prior to the Baseline visit (including hospitalization for any infection in the last 6 months or any current sign or symptom that may indicate an infection).

- 
16. Subjects with a history of herpes zoster infection within 6 months prior to the Baseline visit.
  17. Subjects with known TB infection, at high risk of acquiring TB infection, or LTB infection are excluded.
    - a. Known TB infection whether present or past is defined as:
      - i) Active TB infection or clinical signs and symptoms suspicious for TB (pulmonary or extra-pulmonary)
      - ii) History of active TB infection involving any organ system or findings in other organ systems consistent with TB infection
      - iii) Any evidence by radiography or other imaging modalities consistent with previously active TB infection that is not reported in the subject's medical history.
    - b. High risk of acquiring TB infection is defined as:
      - i) Known exposure to another person with active TB infection within the 3 months prior to Screening
      - ii) Time spent in a healthcare delivery setting or institution where individuals infected with TB are housed and where the risk of transmission of infection is high.
    - c. Latent TB infection (unless appropriate prophylaxis is initiated prior to study treatment and continued to completion of prophylaxis). Please refer to Section 12.6.3 for further details and instructions.
  18. Subjects with concurrent acute or chronic viral hepatitis B or C or with human immunodeficiency virus (HIV) infection.
  19. Subjects with history of or current active infection with Histoplasma, Coccidioides, Paracoccidioides, Pneumocystis, nontuberculous mycobacteria (NTMB), Blastomyces, or Aspergillus.
  20. Subjects must not have a history of an infected joint prosthesis at any time.
  21. Subjects receiving any live (includes attenuated) vaccination within the 8 weeks prior to Baseline (eg, inactivated influenza and pneumococcal vaccines are allowed but nasal influenza vaccination is not permitted).
  22. Subjects who in the Investigator's opinion have a high risk of infection (eg, subjects with leg ulcers, indwelling urinary catheter, persistent or recurrent chest infections, and subjects who are permanently bedridden or wheelchair bound).
  23. Subjects with a history of a lymphoproliferative disorder including lymphoma or current signs and symptoms suggestive of lymphoproliferative disease.
  24. Concurrent malignancy or a history of malignancy (subjects with less than 3 excised basal cell carcinomas or with cervical carcinoma in situ successfully surgically treated more than 5 years prior to Screening may be included).
  25. Subjects with Class III or IV congestive heart failure as per the New York Heart Association (NYHA) 1964 criteria.

- 
26. Subjects with a history of, or suspected, demyelinating disease of the central nervous system (eg, multiple sclerosis or optic neuritis).
  27. Subjects having had major surgery (including joint surgery) within 8 weeks prior to Screening, or having planned surgery within 6 months after entering the study.
  28. Subjects with a current or recent history, as determined by the Investigator, of severe, progressive, and/or uncontrolled renal, hepatic, hematological, endocrine, pulmonary, cardiac, or neurological disease.
  29. Subjects with significant laboratory abnormalities, including but not limited to:
    - liver function tests >2.0xULN
    - estimated Glomerular Filtration Rate as measured by Chronic Kidney Disease Epidemiology Collaboration (CKD-EPI; Levey et al, 2009) <60mL/min/1.73m^2
    - white blood cell ([WBC] <3.0x10^9/L).
  30. Subjects with any other condition which, in the Investigator's judgment, would make the subject unsuitable for inclusion in the study.

### 6.3 Withdrawal criteria

Subjects are free to withdraw from the study at any time, without prejudice to their continued care.

Subjects should be withdrawn from the study if any of the following events occur:

1. Subject develops an illness that would interfere with his/her continued participation.
2. Subject is noncompliant with the study procedures or medications in the opinion of the Investigator.
3. Subject withdraws his/her consent.
4. There is confirmation of a pregnancy during the study, as evidenced by a positive pregnancy test (see [Section 12.1.6](#) for more information regarding pregnancies).
5. The Sponsor or a regulatory agency requests withdrawal of the subject.
6. Subject's subsequent TB test was confirmed positive or any further evidence is suggestive of potential TB infection (eg, exposure). Refer to [Section 12.6.3](#) for further details and instructions.

Subjects should be withdrawn from the study-treatment if,

7. The Investigator decides to initiate an alternative treatment due to an unsatisfactory response to the study treatment, or
8. Subjects take any of the prohibited medications in [Table 7–1](#) and [Section 7.8.2](#)

If a subject is withdrawn from the double-blind study treatment, the Investigator should encourage the subject to continue participation in the study in accordance with the appropriate alternative schedule of study assessments ([Table 5–2](#) or [Table 5–3](#)). The treatment that the subject receives following withdrawal of study medication is at the discretion of the Investigator,

with open-label CZP available as a treatment option according to the local requirement mandated in the region. UCB will provide this medication free of charge. Alternatively, the Investigator may treat the subject with other treatments (including biologics) as deemed appropriate by local regulations. If the Investigator chooses to withdraw subjects on the other therapy, the local guidelines on initiation and monitoring of the particular treatment should be followed.

Investigators should contact the Medical Monitor, whenever possible, to discuss the withdrawal of a subject from the double-blind study treatment in advance. The reason for discontinuation of the double-blind study treatment must be recorded in the case report form (CRF) as appropriate.

Although the subject may be withdrawn from the double-blind study treatment at any time, every effort should be made to retain the subject in the study and encourage compliance of the subject with the scheduled study visits. For subjects who fail to return to study visit(s) or are considered lost to follow up, the Investigator should specifically communicate (at least 1 phone call and 1 written message to the subject), and document his/her effort (date and summary of the phone call and copy of the written message in the source documents). In case the attempts to direct contact the subject fail, the Investigator is encouraged to gain information about the wellbeing of the subject at the end of the regular visit schedule (Week 52/WD) from other sources in compliance with local regulations. All results of observations and communication with the subject, including and not limited to the relevant information on his/her wellbeing, must be recorded in the source documents.

If a subject is withdrawn from the study, the narrative description of the reason(s) for removing the subject must be recorded in the source documents. The CRF must document the primary reason for withdrawal.

Subjects withdrawn from the study will not be replaced.

#### **6.4 Eligibility for the SFE Period**

To be eligible to participate in the SFE Period, subjects on double-blind study treatment and subjects who withdrew from double-blind study treatment and transitioned to open-label CZP treatment must complete all of the Week 52 visit assessments. Subjects on alternative treatments are not eligible to participate in the SFE Period.

Eligible subjects are allowed to roll-over to the SFE-Period up to 3 months after completion of the Week 52 assessments.

Prior to initiating the SFE assessments, all subjects will be asked to read and sign a separate informed consent form.

Questions concerning the eligibility of a subject to continue participation in the study should be made in consultation with the Medical Monitor.

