**Period 3 (Follow-Up Period):**

All subjects not participating in the SFE Period after Week 52, including those withdrawn from the study prematurely, will have a FU visit 8 weeks after the Week 52/WD visit.

**Safety Follow-Up Extension (SFE) Period:** Week 52 to Week 156, open-label.

At the completion of the Week 52 visit assessments, subjects on double-blind study treatment may receive open-label CZP treatment for an additional 2 years. Subjects who withdrew from double-blind study treatment and transitioned to open-label CZP treatment are also eligible to participate in the SFE Period after completing the Week 52 visit assessments. Subjects on alternative treatments are not eligible to participate in the SFE Period.

Eligible subjects are allowed to roll-over to the SFE-Period up to 3 months after completion of the Week 52 assessments.

In order to maintain the blind for subjects completing double-blind treatment, their study treatment will be administered sc at the study site by unblinded, dedicated study personnel on Weeks 52, 54, and 56. Subjects who withdrew from double-blind study treatment and transitioned to open-label CZP treatment do not need to visit the site at Week 54 and Week 56, and should continue their open-label CZP treatment regimen.

For the remainder of the SFE Period, CZP can be administered at the site by dedicated study personnel, or by self-injection of the subject under the supervision of the dedicated study personnel, or subjects may self-administer their study treatment Q2W at home.

Starting at Week 64, all subjects are to visit the site approximately every 12 weeks ( $\pm 2$  weeks) for-assessments.

The last dosing visit will be at Week 154. The final study assessments are performed at Week 156/SFE-WD.

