### **5.1.2 Study duration per subject**

For each subject, the first 3 periods of the study will last a maximum of 66 weeks, as follows:

- Up to 6 weeks in the Screening Period
- 52 weeks in the Double-Blind Period
- A FU visit 8 weeks after the Week 52/WD visit (for subjects not participating in the SFE Period).

For subjects participating in the SFE Period, the study will extend up to a maximum of 104 additional weeks.

The estimated recruitment period is up to 15 months. The first subject first visit is planned in Quarter 3 of 2015. The end of the study will be defined as the date of the last subject's last visit, defined as the FU visit 8 weeks after the Week 52/WD visit for subjects not participating in the SFE Period, or the last visit of the SFE Period

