### 7.2.1 Treatment administration

A pharmacy manual will be provided to each site containing instructions regarding drug preparation and dosing. The injection schedule through Week 52 is presented in Figure 7-1. The injection schedule for the SFE Period is presented in Figure 7-2.

At on-site visit days (at Weeks 0, 2, 4, 6, 8, 10, 12, 16, 20, 24, 28, 32, 36, 40, 44, 48, and 50), the double-blind study treatments will be administered sc at the study site. At the Week 0, 2, 4, 6, and 8 visits, the administration must be done by dedicated, unblinded, and adequately trained site personnel. At the Week 10 and 12 visits, the subject will receive training on self-injection and the study treatment will be self-administered under the supervision of the unblinded study personnel. At Weeks 16, 20, 24, 28, 32, 36, 40, 44, 48, and 50, the study treatment administration should preferably be done by the unblinded study personnel, or alternatively by self-injection of the subject under the supervision of the unblinded study personnel. The double-blind study treatment will be self-injected at home at Weeks 14, 18, 22, 26, 30, 34, 38, 42, and 46.

Injections should be administered with a minimum of 10 days between the CZP 200mg Q2W injections.

[figure not shown]
During the SFE Period, CZP will be administered sc by dedicated unblinded study personnel at the study site on Weeks 52, 54, and 56 for subjects completing double-blind treatment in order to maintain the blind. Subjects who complete the Week 52 Visit on placebo treatment will receive loading doses of CZP 400mg at these visits. Subjects who complete the Week 52 Visit on CZP treatment will receive 1 injection of CZP 200mg and 1 injection of placebo at these visits to continue their previous CZP treatment regimen.

Subjects who withdrew from double-blind study treatment and transitioned to open-label CZP treatment do not need to visit the site at Week 54 and Week 56, and should continue their open-label CZP treatment regimen.

For the remainder of the SFE Period, CZP can be administered at the site by dedicated study personnel, or by self-injection of the subject under the supervision of the dedicated study personnel, or subjects may self-administer their study treatment Q2W at home.

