### **7.8.3 Concomitant medication(s)/treatments during the SFE Period**

At the completion of the Week 52 visit assessments, subjects on double-blind study treatment may receive open-label CZP treatment for an additional 2 years during the SFE Period. During this time, CZP will be provided by the Sponsor. Concomitant medication usage during the SFE Period is at the discretion of the Investigator.

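### A placebo completer who enters the extension late can start certolizumab pegol on a pregnancy test and TB questionnaire about 13 weeks old, because the protocol schedules no repeat before that dose

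*Protocol*

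**What the plan says.** Section 6.4 sets the entry rule: "Eligible subjects are allowed to roll-over to the SFE-Period up to 3 months after completion of the Week 52 assessments". Sections 5.1.1 and 8.6 repeat it. The other stated conditions are completed Week 52 assessments, not being on an alternative treatment, and a new consent form.

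For placebo completers, entry is the first exposure to CZP. Section 7.2.1 says of the first three extension dosing visits: "Subjects who complete the Week 52 Visit on placebo treatment will receive loading doses of CZP 400mg at these visits".

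In the 52/0 column, Table 5-6 marks only consent, the interactive response system, loading-dose administration and dispensation. The table has no row for a pregnancy test, a TB questionnaire or concomitant medication. Its footnote a points back to the earlier visit: "Assessments performed at the Week 52 Visit for subjects who completed the previous Double-Blind Period are in Table 5-1". No repeat is asked for when entry is delayed.

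Section 8.6 adds no such check. Sections 12.6.1 and 12.6.3.1 recommend pregnancy and TB testing in the SFE under local practice, without a time point. Section 7.8.3 says: "Concomitant medication usage during the SFE Period is at the discretion of the Investigator".

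**The concern.** The Week 52 visit serves as the safety check for starting CZP in the extension. That works when the first dose is given at that visit. It does not work when the dose may follow up to 3 months later, because pregnancy and TB exposure can both arise in the interval and nothing scheduled looks for them.

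The protocol itself treats these checks as conditions of starting CZP. Section 12.6.3 explains why TB matters: this drug class carries a significant risk of reactivating latent infection. The subject most affected is the placebo completer, for whom the delayed dose is the first anti-TNF dose in the trial. What is at stake is subject safety at that dose, not the efficacy result.

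**Working it through.** The protocol gives no maximum age for these checks before an SFE dose, so there is no figure of its own to reproduce. The test is to compare the protocol's CZP starting points and then work out how old the checks can be.

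**Checks scheduled at the visit where CZP is started**

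| CZP start | Source | Pregnancy test | TB questionnaire |
|---|---|---|---|
| Baseline | Section 8.2 | Required | Required |
| Switch to open-label CZP (wdt Week 0) | Section 8.9, Table 5-4 | Required | Required |
| Same switch, started on a later day | Section 5.2 | Required at the return visit | Required at the return visit |
| SFE entry at the Week 52 visit | Section 8.5 | Required | Required |
| SFE entry up to 3 months later | Section 8.6, Table 5-6 | Not scheduled | Not scheduled |

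The third row is the closest parallel. When a switch to open-label CZP is decided at one visit and begun shortly afterwards, Section 5.2 has the subject complete the full wdt Week 0 list on the day of starting. A much longer delay into the SFE triggers no such list.

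**Age of the last scheduled check**

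Inputs: a gap of up to 3 months (Sections 5.1.1, 6.4, 8.6); last scheduled urine pregnancy test and TB questionnaire at Week 52 (Section 8.5).

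- Gap in weeks: 3 × (365.25 / 12) / 7 = 13.04, taken as 13.
- Latest first SFE dose: 52 + 13 = Week 65.
- Age of the pregnancy test: 65 − 52 = 13 weeks.
- Age of the TB questionnaire: 65 − 52 = 13 weeks.

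For comparison, Baseline repeats both checks even though Screening can be no more than 6 weeks earlier (Sections 8.1 and 8.2). The delayed SFE start tolerates 13 / 6 = 2.2 times that interval with no repeat.

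**Two choices behind these figures**

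- Follow-up visit. Section 8.7 includes a serum pregnancy test 8 weeks after Week 52, but only for subjects not participating in the SFE. A planned late entrant has no such visit, so it is not credited here.
- TB questionnaire at Week 52. The Summary appears to limit it to subjects not entering the SFE, whereas Sections 8.5, 12 and 12.6.3.4 carry no such limit. The 13-week figure uses Section 8.5, the reading more favourable to the plan.

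**The case against.** The strongest reply is that monitoring in the SFE was deliberately left to local practice (Section 2.5) and that real safeguards remain. Section 6.1 requires contraception throughout the study and for a period after the last dose. Section 6.3 withdraws subjects with a positive pregnancy test or evidence of TB infection or exposure. Section 7.8.2 requires withdrawal before any live vaccine is given. Section 6.4 directs eligibility questions to the Medical Monitor, and Section 12 has adverse events solicited at every visit. The protocol also accepts long intervals elsewhere: the TB questionnaire goes from Week 36 to Week 52 (52 − 36 = 16 weeks) during treatment, and the regular schedule has no pregnancy test between Baseline and Week 52.

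Much of this stands and limits how serious the point is. It does not remove it. The withdrawal rules act on a result or on known exposure, but they do not schedule the test or the questions. The long intervals apply to subjects already on study treatment, whereas the gap here is before a first CZP dose.

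A reader might infer several stronger points that the documents do not support:

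- **A live vaccine given in the gap is uncontrolled.** Exclusion 21 ("Subjects receiving any live (includes attenuated) vaccination within the 8 weeks prior to Baseline") is indeed tied to Baseline. But the Section 7.8.2 withdrawal rule applies during the study and has such vaccines recorded in the case report form, and Section 7.8 requires a running medication record.
- **A late entrant cannot follow the loading schedule.** Footnote d of Table 5-6 does say "At Weeks 52, 54, and 56, study treatment administration should be performed at the site by unblinded study personnel". The same columns are also labelled SFE Weeks 0, 2 and 4, which a late entrant can follow from entry.
- **Late entry shortens extension treatment.** "The last dosing visit will be at Week 154" and "For subjects participating in the SFE Period, the study will extend up to a maximum of 104 additional weeks" could be read that way. But the protocol does not say whether late entrants follow the overall study week or the SFE week, so any exposure range depends on a choice of clock that the text does not make.
- **All Section 6.2 exclusions should be reviewed again.** That would be a new eligibility gate, and nothing in the text shows that one was intended.

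**Conclusion.** The point holds in a narrow form. Followed as written, the protocol lets a placebo completer start CZP up to about 13 weeks after the last scheduled pregnancy test and TB questionnaire, although both are required at the starting visit for its other CZP starts. This is a safety gap in the schedule for delayed entrants, partly offset by the existing safeguards.

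The figure assumes that 3 months is 13 weeks, that no follow-up visit takes place, and that the Week 52 questionnaire is completed as Section 8.5 lists it. On-time entrants are not affected. The number of late entrants is not given, so the overall impact cannot be sized. The Week 52 efficacy analysis is unaffected. The change is a worthwhile low-cost improvement, not a threat to the trial's conclusions.

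**What to change.** Amend Sections 6.4 and 8.6 and Table 5-6. For any subject whose first SFE dose is not given at the Week 52 visit, require before dosing:

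- a urine pregnancy dipstick for women of childbearing potential;
- the TB questionnaire;
- a brief query on adverse events, concomitant medication and vaccines since Week 52.

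The dipstick and questionnaire are already used in the trial. The vaccine question simply confirms that the Section 7.8.2 rule was followed during the gap.

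The cost is amendment wording plus one dipstick, one questionnaire and a few questions for late starters only. The downside is a slightly longer first SFE visit for them. No change to the dosing schedule, visit weeks or analysis is needed.
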